## STATISTICAL METHODS

Maximum 60 patients are planned for enrollment into this clinical trial.

Safety Analysis. All patients who receive at least one dose of the investigational treatment will be included in the safety population. All safety analyses will be performed on the safety population. Adverse Events (AE) will be coded according to the MedDRA adverse event dictionary. The results will be tabulated to examine their frequency, organ systems affected, and relationship to study treatment. The results of laboratory tests will be evaluated similarly.

Efficacy Analysis. Efficacy results, including but not limited to ORR24, BORR, DOR, DCR, TTR, PFS, and OS for patients enrolled into Part A will be provided using descriptive statistics. Objective responses will be evaluated according to both RECIST v1.1 and Response Evaluation Criteria In Solid Tumors for Immunotherapeutics (iRECIST).

Note: Confirmatory scans are required for all determinations of objective response (PR or CR), Stable disease(SD) and disease progression (PD). Confirmatory scans must be performed at least 4 weeks later.

Part B follows a Simon Two-Stage mini-max design. The sample size for the first stage of Part B is 15 patients; the sample size for the second stage is 13 patients, for a total of 28 patients. Patients from Part A without a DLT, who receive the recommended Phase 2 treatment regimen and who are considered evaluable for efficacy will be included in the analysis for Part B Stage 1. For a null hypothesis ORR24 of 0.15 and an alternative hypothesis ORR24 of 0.35, the sample size of 28 subjects will provide a one-sided significance level of 5% and a power of 80%. For Stage 1, a minimum of three patients must demonstrate a response (PR or better) to proceed to the second stage. Study has passed the first stage of Simon-Two stage design. If Stages 1 and 2 are completed, a minimum of 8 patients must demonstrate a response (PR or better) to reject the null hypothesis. If a patient's responses could not be confirmed, that patient will not be included in the primary efficacy population for ORR24.

Part C is to evaluate efficacy in larger patient population.

In Keynote-158 study (pembrolizumab monotherapy in patients who have progressed with standard of care systemic therapy), ORR in total patients (i.e. regardless of PD-L1 status) and with CPS  $\geq 1$  were 12.2% and 14.6%, respectively.

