RECIST v1.1 Definitions for the Evaluation of Overall Response

Target lesions	Non-Target lesions	New Lesions	Overall response
CR	CR	No	CR
CR	Incomplete response/SD	No	PR
PR	Non-PD	No	PR
SD	Non-PD	No	SD
PD	Any	Yes or No	PD
Any	PD	Yes or No	PD
Any	Any	Yes	PD

ORR is defined as the proportion of efficacy evaluable patients (see Section 24.3) with a tumor size reduction that meets the RECIST v1.1 Overall Response definition of a Partial Response (PR) or Complete Response (CR). If a CR has been confirmed for a patient, the sponsor will

discuss with the patient's investigator whether the study treatments need to be continued or not.

If a patient's responses could not be confirmed, that patient will not be included in the primary efficacy population for ORR24.

In addition, efficacy endpoints will also be determined using the immune-related RECIST (iRECIST) (please refer to Appendix 6).

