Statistical Methods for Efficacy & Immunogenicity/ Analyses	Efficacy Analyses. Descriptive statistics will be employed to analyze the efficacy data. It also provides subject plots for individual patients. Summary statistics for continuous variables will include the mean, standard deviation, median, interquartile range, and range (minimum/maximum). Categorical variables will be presented as frequency counts and percentages, and time-to-event variables will be summarized with number of non-missing observations, median survival time, and survival probability using Kaplan-Meier method if applicable. Kaplan Meier plot will also be provided.		
	Immunogenicity Analyses. Immunogenicity will be described to explore humoral and cellular immune responses to GX-188E and P (e.g., antibodies to E6 and E7 and the number of antigen-specific IFN-γ secreting T lymphocytes in samples of PBMC) in blood samples obtained from study subjects		
Treatment Assignment	All participants will be allocated GX-188E + pembrolizumab		
Statistical Methods for Safety Analyses	Summary statistics will be provided for the safety endpoints as appropriate.		
Interim Analyses	An interim analysis will be performed with safety and efficacy data in case of at least 22 patients in efficacy evaluable population, after obtaining week 10 tumor assessment results (either by investigator/BICR).		
Final Analysis	The final analysis will be performed to report a primary CSR based on a data cut off after all 60 patients in the planned efficacy evaluable population have completed tumor assessment within 24 weeks by the investigator per RECIST v1.1 Since patient will be treated until they met one of the discontinuation criteria, some patients may still be ongoing at the time of final analysis. Therefore, a long-term follow-up study can be performed after final analysis with all available data (no cut-off date applied).		
Multiplicity	No multiplicity adjustment is planned in this trial.		
Sample Size and Power	Part A Safety Evaluation: For Part A, the goal is to determine a treatment schedule for which the rate of DLTs is less than 33% in 6 or 9 patients. A minimum of 6 patients		

are planned with a maximum of 18 DLT-evaluable patients for the Starting Treatment Schedule and Reduction Level 1

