## Part B. Exploratory Efficacy Evaluation in Advanced Cervical Cancer Patient (Simon Two-Stage Design)

In Part B, patients will receive the treatment schedule for GX188E + P that was determined from Part A to be well-tolerated. In the first stage of Part B, 15 patients with advanced HPV 16 or 18 positive cervical cancer will be treated. If at least 3 patients experience an objective response (i.e. partial response or better) by RECIST v1.1 in the first 24 weeks of treatment, an additional 13 patients will be enrolled for a total of 28 patients in Part B. If 2 or fewer patients in the first stage experience an objective response, enrollment into Part B will be discontinued for futility. Study has passed the first stage of Simon-Two stage design.

Sample Size for Part B: Part B follows a 1-sided Simon 2-Stage minimax design; 15 patients, including all patients from Part A without a DLT, who receive the recommended Phase 2 regimen and who meet the criteria for the Efficacy Evaluable Population with HPV 16 or 18 positive advanced cervical cancer will be included in the first stage analysis. If 3 or more objective responses (Partial response or better) are observed in the first stage, another 13 patients will be enrolled into the second stage, for a total of 28 patients in Part B. Study has passed the first stage of Simon-Two stage design. For a null hypothesis ORR24 of 0.15 and an alternative hypothesis ORR24 of 0.35, the sample size of 28 patients will provide a one-sided significance level of approximately 5% and a power of 80%. If Stages 1 and 2 are completed, a minimum of 8 patients must demonstrate a response (partial response or better) to reject the null hypothesis. If a patient's response could not be confirmed, that patient will not be included in the primary efficacy analysis for ORR24.

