#### 15. EFFICACY OUTCOMES

Tumor response to treatment will be evaluated using both RECIST v1.1 and iRECIST. For each patient with objectively measurable disease and who meet the criteria for inclusion in the Efficacy Evaluable population, response to therapy will be calculated. The analysis of ORR24, BORR and DCR per RECIST v1.1 will also be performed in safety population as sensitivity analysis.

RECIST 1.1 will be used by BICR as the primary measure for assessment of tumor response, date of disease progression, and as a basis for all protocol guidelines related to disease status (e.g., discontinuation of study treatment). All efficacy endpoints will be evaluated and categorized using RECIST 1.1. Confirmatory scans are required for all determinations of objective response [Partial response (PR) or Complete response (CR)], Stable disease (SD) and disease progression (PD). Confirmatory scans must be performed at least 4 weeks later.

Investigator assessment of tumor response based upon RECIST v1.1 will be analyzed in the same way as the corresponding BICR-assessed endpoints (except Kaplan-Meier curves which will only be presented for BICR assessment). Concordance between BICR and Investigator assessments will be summarized at a patient level for BOR.

iRECIST is based on RECIST 1.1, but adapted to account for the unique tumor response seen with immunotherapeutic drugs. iRECIST will be used by the investigator to assess tumor response and progression and make treatment decisions. When clinically stable, participants should not be discontinued until progression is confirmed by the Investigator, working with local radiology, according to the rules outlined in Appendix 6 of protocol. This allowance to continue treatment despite initial radiologic PD takes into account the observation that some participants can have a transient tumor flare in the first few months after the start of immunotherapy, and then experience subsequent disease response. This data will be captured in the clinical database.

Efficacy endpoints are as follows.

- Objective Response Rate within 24 weeks (ORR24)
- Best Overall Response Rate (BORR)
- Progression-Free Survival including 6-month PFS rate and median PFS time
- Overall Survival including 6-month OS rate and median OS time
- Disease Control Rate
- Duration of Response
- Time to Best Response

Document: \(\)\ieedc-vnac01\\Biosdata\\Genexine\\GX-188E\\GYA02599\\Biostatistics\\Documentation\\SAP\)

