#### **15.1.** PRIMARY EFFICACY ENDPOINTS

The primary efficacy variable is BICR-assessed ORR24 by RECIST 1.1 in Part B and C.

Best overall response within 24 weeks (BOR24) is the best objective response achieved within the first 24 weeks of treatment prior to study discontinuation. All available response designations will contribute to the BOR24 determination. If a patient's BOR24 could not be confirmed, that patient will not be included in the primary efficacy population for ORR24. Additional patients will be enrolled to meet the study hypothesis. Any CR or PR must be confirmed by a sequential assessment that is at least 4 weeks apart. The confirmation rule is defined in Table 2 (please refer to RECIST 1.1 [1]). The confirmed response will be determined before analysis. The number and percentage of patients in each category of best overall response CR, PR, SD, PD or Not Evaluable (NE) will be provided.

ORR24 is the proportion of efficacy evaluable patients who achieve an objective response (PR or CR) within 24 weeks prior to study discontinuation. The number and percentage of patients who achieve best overall response of PR or CR will be summarized.

If the first responses can be confirmed by the second response within 24 weeks of treatment. they will be included as responses for ORR24. Also, If the first response within 24 weeks is confirmed by the second response after 24 weeks of treatment, the first response should be included as response for ORR24.

Table 2. Best overall response when confirmation of CR and PR is required per RECIST 1.1 Guideline

Overall response  First time point	Overall response Subsequent time point	Best overall response
CR	CR	CR
CR	PR	PR, or SD provided at least 28 days' duration, otherwise PD a
CR	SD	SD provided at least 28 days' duration, otherwise PD

Document: \(\)\ieedc-vnac01\\Biosdata\\Genexine\\GX-188E\\GYA02599\\Biostatistics\\Documentation\\SAP\)

Author: [name] Version Number: 1.1

Version Date: 05Sep2022

Template No: CS TP BS016 Revision 6 Reference: CS WI BS005

Analysis Plan Page 29 of 48

CR	PD	SD provided at least 28 days' duration, otherwise PD
CR	NE	SD provided at least 28 days' duration, otherwise NE
PR	CR	PR
PR	PR	PR
PR	SD	SD
PR	PD	SD provided at least 28 days' duration, Otherwise PD
PR	NE	SD provided at least 28 days' duration, Otherwise NE
NE	NE	NE

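### SAP 15.1 drops patients whose BOR24 is unconfirmed from the ORR24 population and enrols others, while SAP Table 2 keeps them as non-responders; applied as written, the exclusion biases the primary endpoint upward

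*SAP*

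**What the plan says.** **The exclusion.** SAP 15.1 says: "If a patient's BOR24 could not be confirmed, that patient will not be included in the primary efficacy population for" ORR24. The next sentence is: "Additional patients will be enrolled to meet the study hypothesis". The exclusion also stands in SAP 3.1 under Part B ("If a patient's response could not be confirmed, that patient will not be included in the primary efficacy analysis for" ORR24), in Protocol 22.2 ("If a patient's responses could not be confirmed, that patient will not be included in the primary efficacy population for" ORR24), and in the Statistical Methods part of the Protocol 7.0 synopsis.

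**The competing rule.** SAP 15.1 also defines ORR24 as a proportion of efficacy evaluable patients. The definitions of that population (Protocol 24.4, SAP 5.4) contain no confirmation condition. SAP 15.1 requires: "Any CR or PR must be confirmed by a sequential assessment that is at least 4 weeks apart". Table 2 then classifies an unconfirmed response:

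- PR then SD is SD.
- PR then PD is SD or PD.
- PR then NE is SD or NE.

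The text under Table 2 classifies patients with a single scan as PD, SD or NE, and NE is one of the tabulated categories. Under these rules such patients stay in the analysis as non-responders.

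**Sample size.** The Protocol synopsis says: "Maximum 60 patients are planned for enrollment into this clinical trial". Protocol 24.1 sets the final analysis "after all 60 patients in the planned efficacy evaluable population have completed tumor assessment within 24 weeks". Protocol 24.8 and SAP 4.3 set the same trigger.

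**The concern.** Under the exclusion, whether a patient is analysed depends on her outcome. The numerator holds only confirmed CR or PR, and a first response within 24 weeks that is confirmed later still counts. Removing unconfirmed patients therefore leaves the numerator unchanged and takes only non-responders out of the denominator.

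The documents also leave open whom the rule reaches.

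- **Narrow reading:** unconfirmed CR or PR only, as the confirmation sentence in SAP 15.1 and Table 2 suggest.
- **Wider reading:** unconfirmed SD and PD too. The Protocol synopsis, Protocol 22.1.2, the imaging footnotes in Appendix 1 and SAP 15 ask for confirmatory scans for SD as well as response, and all but 22.1.2 name PD there too. Appendix 5 names CR, PR and PD. This reading could remove progressors who never had a repeat scan. Protocol 22.3 and Table 6 do not require one in clinically unstable patients, though that text concerns investigator iRECIST, not the BICR RECIST 1.1 endpoint.

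At stake are the Part C test against 12.2% and the Part B gate of at least 8/28 that opens Part C.

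**Working it through.** **Inputs from the documents.** Part C: null 12.2%, alternative 37%, two-sided 0.05, 97% power, 25% dropout, N = 60; success if the Clopper-Pearson 95% lower bound exceeds 12.2% (Protocol 24.3, SAP 3.1). Part B: at least 3/15, then at least 8/28; null 15%, alternative 35%. Protocol 10.5 gives an analysed range of 45 to 60.

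**Assumed.** q, the share of non-responders removed, is not in the documents. I use 5% as a low case for the narrow reading, then 10, 20, 30 and 40%.

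**Step 1: reproduce the plan.** With 45 analysed, 10/45 has lower bound 11.20% and 11/45 has 12.88%, so success needs at least 11. Power at 37% is 97.4%, and 45/(1 − 0.25) = 60. The Part B rule has one-sided error 4.6% at 15% and power 80.3% at 35%. Both agree with the stated designs. With 60 analysed, 13/60 has lower bound 12.07% and 14/60 has 13.38%, so success needs at least 14.

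**Step 2: removal with replacement.** If a share q of non-responders is removed and replaced, the response rate among those analysed is

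p_eff = p / [p + (1 − p)(1 − q)].

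For p = 0.122 and q = 0.20: 0.122 / (0.122 + 0.878 × 0.80) = 0.122 / 0.8244 = 0.148. The chance of success is the binomial upper tail at p_eff; for Part B the two-stage rule is evaluated at the p_eff obtained from p = 0.15.

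**Step 3: removal without replacement.** With 60 enrolled, X ~ Bin(60, 0.122) responders and D ~ Bin(60 − X, q) removed, success means the lower bound for X/(60 − D) exceeds 12.2%.

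| q | p_eff (Part C) | ≥14/60, replaced | ≥11/45, replaced | 60 enrolled, not replaced | Part B gate, true 15% |
|---|---|---|---|---|---|
| 0 | 12.2% | 1.2% | 1.7% | 1.2% | 4.6% |
| 5% | 12.8% | 1.7% | 2.3% | 2.6% | 5.7% |
| 10% | 13.4% | 2.5% | 3.2% | 3.3% | 7.2% |
| 20% | 14.8% | 5.3% | 6.0% | 6.2% | 11.3% |
| 30% | 16.6% | 11.1% | 11.4% | 10.7% | 17.9% |
| 40% | 18.8% | 22.7% | 21.4% | 17.8% | 28.2% |

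With replacement, the 2.5% upper tail is passed at about q = 10% (N = 60) or 6% (N = 45). Part B passes 5% at about q = 2%.

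**Step 4: single data sets.** 13/60 fails (12.07%); after one exclusion 13/59 passes (12.29%). With replacement, 14/60 passes (13.4%); if six removed patients had been kept as non-responders, 14/66 fails (12.1%).

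**Step 5: enrolment.** Expected enrolment to reach 60 analysed is 60 / [0.122 + 0.878(1 − q)]. At q = 10% this is 60/0.9122 = 65.8. At 20, 30 and 40% it is 72.8, 81.5 and 92.5. The stated maximum is 60.

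**The case against.** The strongest reply is that the SAP's own derivation rules favour the narrow reading. Table 2 is about confirming CR and PR, and the text below it lets one PD scan stand as PD. No passage asking for SD or PD scans says that a missing scan removes the patient. On that reading few patients may go: at 5%, Part C with replacement stays under 2.5% (1.7% or 2.3%), and Part B is 5.7% against a stated level of approximately 5%. This stands, and the larger shares are hypothetical. Removing 40% of non-responders would be 0.878 × 40% = 35% of all patients at the null, above the planned 25% dropout.

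The 13/60 against 13/59 contrast is partly binomial discreteness: a plain 59-patient trial also passes at 13, with an upper tail of 2.4%. That is so, but here the outcome would decide which denominator applies.

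Three other points do not change the conclusion.

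- **Room under the cap.** Extra patients could fit within 60 if only 45 were analysed. The final-analysis text, however, requires all 60 in the efficacy evaluable population.
- **Removing a true responder.** A PR followed by an unconfirmed CR is a PR under Table 2, so it is not an unconfirmed BOR24. A response still awaiting confirmation is already SD or NE under Table 2 and the single-scan rule.
- **Safeguards.** Agreeing populations before database lock (SAP 5) and repeating ORR24 in the safety population (SAP 15) may expose the effect. Neither corrects the primary test.

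**Conclusion.** The concern holds and must be fixed. The exclusion appears in four places across both documents. It contradicts Table 2, the single-scan rules, the reported NE category and the efficacy evaluable denominator. If it is applied, the bias in ORR24 relative to the confirmed-response endpoint is upward on either reading. If Table 2 is applied, this bias does not arise.

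The direction needs no assumption; the size depends on the assumed share removed. With few removals the effect on Part C error is small, though it can still decide a borderline result. From about 10% of non-responders with 60 analysed and replacement, or about 6% with 45, false success exceeds the intended upper-tail level.

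**What to change.** 1. Delete the exclusion sentence in the Protocol 7.0 synopsis, Protocol 22.2, SAP 3.1 and SAP 15.1.
2. Delete the SAP 15.1 sentence on enrolling additional patients, which also conflicts with the maximum of 60.
3. State that Table 2 and the rules beneath it govern BOR24. Efficacy evaluable patients with unconfirmed CR or PR, SD, PD (confirmed or not) or NE stay in the ORR24 denominator as non-responders.
4. State that for BICR RECIST 1.1 ORR24 confirmation is needed only for CR and PR. Reconcile with this, for the analysis only, the SD and PD confirmation text in the Protocol synopsis, Protocol 22.1.2, the Appendix 1 imaging footnotes, Appendix 5 and SAP 15.

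This is an analysis rule and proposes no change to imaging or treatment decisions. The cost is wording in the two documents, with no new data or patients. The reported ORR24 may be somewhat lower than under the exclusion.

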#### 10.5 Number of Patients

Maximum 60 patients are planned for recruitment to both Parts A, B and C of this study. As previously described in Section 10.2 above, minimum of 6 patients will be enrolled into Part A. The maximum number of safety evaluable patients to be enrolled into Part A is 18.

Part B of this study employs a Simon-Two Stage Design. A minimum of 15 efficacy evaluable patients (see Section 24.4), which may include some patients from Part A, will be included in the analysis for Stage 1. If 3 or more patients in Stage 1 experience objective responses (i.e., Partial Response or better), the study will move into Part B Stage 2 and an additional 13 patients

will be treated, for a total of 28 efficacy evaluable patients. Study has passed the first stage of Simon-Two stage design.

If at least 8 of the 28 subjects enrolled in Part B, experience an objective response who are considered evaluable for efficacy, it will be considered that ORR satisfies the criteria for study expansion and additional 17 subjects (at least) will be enrolled in Part C to evaluate efficacy further in larger population (N=45~60). Refer to the Section 24.3 Sample Size and Power for detailed assumptions for sample size estimation.

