#### 24.3 Sample Size and Power

**Part A Safety Evaluation:** For the traditional 6+3 design of Part A, the goal is to determine a treatment schedule for which the rate of DLTs is less than 33% in 6 or 9 patients. A minimum of 6 patients are planned for Part A, with a maximum of 18 DLT-evaluable patients for the Starting Treatment Schedule and Reduction Level 1. If  $\geq$ 3 in 6 or 9 patients at Reduction Level 1 have DLTs, then the investigational treatment regimen will be considered too toxic and enrollment into the study will be discontinued.

Part B: Part B follows a 1-sided Simon 2-Stage design; 15 patients, including all patients from Part A without a DLT, who receive the recommended Phase 2 regimen and who meet the criteria for the Efficacy Evaluable Population (see Section 24.4), with HPV 16 or 18 positive advanced cervical cancer will be included in the first stage analysis. If 3 or more objective responses (PR or better) are observed in the first stage, another 13 patients will be enrolled into the second stage, for a total of 28 patients in Part B. Study has passed the first stage of Simon-Two stage design. For a null hypothesis ORR24 of 0.15 and an alternative hypothesis ORR24 of 0.35, the sample size of 28 patients will provide a one-sided significance level of approximately 5% and a power of 80%. If Stages 1 and 2 are completed, a minimum of 8 patients must demonstrate a response (PR or better) to reject the null hypothesis.

Part C: Part C is to evaluate efficacy in larger patient population. In Keynote-158 study (pembrolizumab monotherapy in patients who have progressed with standard of care systemic therapy), ORR in total patients (i.e. regardless of PD-L1 status) and with CPS  $\geq$  1 were 12.2% and 14.6%, respectively.

Given this, null hypothesis for  $ORR_{24}$  was set at  $P_0 = 12.2\%$ . With an alternative hypothesis for  $ORR_{24}$  of  $P_a = 37\%$ , the sample size of 60 subjects was calculated considering two-sided significance level of 0.05, 97% power, and 25% dropout rate.

The confidence interval (CI) for ORR24 will be estimated using exact Clopper-Pearson method, and if the lower bound of the two-sided 95% CI for ORR24 exceeds 12.2%, it will be proven to satisfy the primary efficacy.

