#### Part C. Efficacy Evaluation in Larger Number of Patients

If at least 8 of the 28 patients enrolled in Part B, experience an objective response who are considered evaluable for efficacy, it will be considered that objective response rate (ORR) satisfies the criteria for study expansion and additional 17 patients (at least) will be enrolled in Part C to

 $Document: \underline{\label{locality} Nocumentation} Biosdata \underline{\label{locality} GX-188E\underline{\label{locality} GYA02599\underline{\label{locality} Biosdata}} \\$ 

Author: [name] Version Number: 1.1

Version Date: 05Sep2022

Template No: CS\_TP\_BS016 Revision 6 Reference: CS\_WI\_BS005

PROTOCOL GX-188E-005

Analysis Plan Page 13 of 48

evaluate efficacy further in larger patient population (N=60). If only 7 or fewer patients in Part B experience an objective response, enrollment to Part C will not open.

Sample Size for Part C: Part C is to evaluate efficacy in larger patient population. In Keynote-158 study (pembrolizumab monotherapy in patients who have progressed with standard of care systemic therapy), ORR in total patients (i.e. regardless of PD-L1 status) and with CPS  $\geq$  1 were 12.2% and 14.6%, respectively.

Given this, null hypothesis for  $ORR_{24}$  was set at  $P_0$  = 12.2%. With an alternative hypothesis for  $ORR_{24}$  of  $P_a$  = 37%, the sample size of 60 subjects was calculated considering two-sided significance level of 0.05, 97% power, and 25% dropout rate.

The confidence interval (CI) for  $ORR_{24}$  will be estimated using exact Clopper-Pearson method, and if the lower bound of the two-sided 95% CI for  $ORR_{24}$  exceeds 12.2%, it will be proven to satisfy the primary efficacy. And it will be analyzed using two-sided exact binomial test for a null hypothesis for  $ORR_{24}$  of  $P_0$  = 12.2% with a significance level of 0.05.

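### SAP 15.1 ties extra enrolment to unconfirmed responses without a target number or cap, and the documents do not otherwise fix the Part C sample size, so the error rate of the fixed-N test against 12.2% is not guaranteed

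*SAP*

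**What the plan says.** In its definition of the primary endpoint, SAP 15.1 first removes some patients: "If a patient's BOR24 could not be confirmed, that patient will not be included in the primary efficacy population for ORR 24". The next sentence reads: "Additional patients will be enrolled to meet the study hypothesis". It gives no number, upper limit or time of decision, and does not say who decides or what they may know.

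The Part C size appears elsewhere in forms that do not agree:

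- SAP 3.1: "additional 17 patients (at least) will be enrolled in Part C", for a total of 60. Protocol 7.0 has the same minimum and total.
- Protocol 10.5: "additional 17 subjects (at least) will be enrolled in Part C", but with the total given as a range: "will be enrolled in Part C to evaluate efficacy further in larger population (N=45~60".
- Protocol 7.0, Statistical Methods: "Maximum 60 patients are planned for enrollment into this clinical trial". Protocol 10.5 also sets a maximum of 60.
- Protocol 24.3: "the sample size of 60 subjects was calculated considering two-sided significance level of 0.05, 97% power, and 25% dropout rate".
- Protocol 24.1 and 24.8 and SAP 4.3: the final analysis follows once all 60 patients in the efficacy population have had their 24-week assessment.

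Success is declared "if the lower bound of the two-sided 95% CI for ORR 24 exceeds 12.2" percent (Protocol 24.3), supported by a two-sided exact binomial test at 5%. SAP 4 plans one interim and one final analysis. SAP 7.4 plans no multiplicity adjustment.

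**The concern.** A Clopper-Pearson bound and an exact binomial test have their stated error rate when N is set independently of the responses. SAP 15.1 gives the hypothesis as the reason for enrolling more patients, where one would expect a target count, and the trigger is whether a response was confirmed. That differs from the replacement rule in Protocol 24.4, which turns on toxicity, 45 days of treatment and having a post-baseline assessment.

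Responses can be known while enrolment is open. The trial is open-label, investigators assess response to manage treatment (Protocol 22.3), and the interim analysis includes efficacy (SAP 4.2). Central review of the endpoint does not blind the decision to enrol.

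The primary claim rests on one bound in a single-arm trial. If N can move with the responses, the sponsor cannot show that it did not. Any stopping on success would raise the false-positive rate and bias the reported response rate upward.

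**Working it through.** **Inputs.** Null rate 12.2%, alternative 37%, two-sided 5% (upper tail 2.5%), 97% power, 25% dropout (Protocol 24.3). Part B gates: at least 3 responders of 15, then at least 8 of 28 (Protocol 10.3 and 10.4). Part C adds at least 17, and 28 + 17 = 45.

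**1. The plan's own figure.** Find the smallest x whose Clopper-Pearson 95% lower bound exceeds 0.122, then compute P(X ≥ x) for X ~ Bin(n, p).

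- n = 45: x = 11 (bound 0.1288). Error at p = 0.122 is 0.0173; power at p = 0.37 is 0.974.
- Allowing for dropout: 45 / (1 − 0.25) = 60.

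The stated design therefore reproduces as 45 evaluable and 60 enrolled, with 97.4% power against the stated 97%.

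**2. Do the other statements of N agree?** If 60 must be evaluable, as the final-analysis text says, enrolment at 25% dropout is 60 / 0.75 = 80, which exceeds the maximum of 60. At n = 60, x = 14 (bound 0.1338), error is 0.0119 and power 0.992. The documents thus carry two different evaluable targets, 45 and 60, and only 45 fits the cap and the dropout allowance.

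**3. What could stopping on success do?** Start at n = 45 and carry the exact distribution of the responder count forward one patient at a time at p = 0.122. At each look, remove and add up the probability at or above the threshold for that n. The gated column also discards paths with fewer than 3 responders at 15 or fewer than 8 at 28, and pools those 28 patients into N.

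| Rule | Error, gates ignored | Error, gates binding |
|---|---|---|
| Fixed N = 45 | 1.73% | 0.68% |
| Fixed N = 60 | 1.19% | 0.39% |
| Looks at 45 and 60 | 2.18% | 0.73% |
| Looks at 45, 50, 55, 60 | 2.52% | 0.78% |
| Every patient, 45 to 60 | 3.57% | 0.89% |
| Every patient, 45 to 75 | 4.49% | 0.93% |
| Every patient, 45 to 100 | 5.80% | 0.97% |

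The last two rows need more than 60 patients and so break the stated maximum.

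**4. Is deleting the sentence enough?** No. SAP 15.1 would still drop patients with an unconfirmed response, so evaluable N would still vary with an outcome. The exclusion also conflicts with SAP Table 2 and the text after it, which already assign an unconfirmed CR or PR to SD, PD or NE. Those are non-responder categories that stay in the denominator.

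**The case against.** In context the sentence is mainly a top-up rule. It follows an exclusion, and the natural reading is that excluded patients are made up so that the planned number is reached. The protocol already allows non-evaluable patients to be replaced and already allows for dropout, which explains 45 and 60. Enrolment is capped at 60. One final test is planned, triggered by a patient count. The only interim, from 22 evaluable patients with week 10 data, has no test of the 12.2% null attached. Protocol 22.1.2 says that response does not typically need real-time central verification.

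Most of this stands. A reader might infer that the SAP instructs the sponsor to keep enrolling until the lower bound passes 12.2%, and that the test has lost its error rate. The documents do not support that: no text prescribes testing until success, and no look between 45 and 60 is planned. Within the cap, looks every five patients leave the error essentially at 2.5%.

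Two parts do not stand. The top-up reading still leaves confirmation of response as the trigger. And the cap cannot be relied on to limit the sentence, because the plan's own final-analysis trigger of 60 evaluable patients exceeds it at the planned dropout.

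**Conclusion.** The enrolment sentence is uncapped and tied to an outcome, and no other section fixes N. The error rate is therefore not guaranteed, which is weaker than saying it is badly inflated. Within 60 patients, stopping on success gives between 2.2% and 3.6% against a nominal 2.5%. With the Part B gates binding and the 28 patients pooled, it stays below 1%. Figures such as 4.5% by 75 patients or 5.8% by 100 would apply only if the maximum were exceeded and the gates did not bind.

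These results assume independent responses with a common rate of 12.2% and a first look at 45. Pooling of Part B is inferred from 28 + 17 = 45. The plan does not present the gates as error control for the Part C test, so the ungated column is the cautious one. The stopping schedules are what the wording leaves open; the plan describes none of them.

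**What to change.** - Delete the enrolment sentence from SAP 15.1.
- State one target evaluable N (45, with 97.4% power by the exact test) and one maximum enrolled (60). Reconcile Protocol 7.0, 10.5, 24.1 and 24.8 and SAP 3.1 and 4.3 to these two numbers, saying each time whether the figure means enrolled or evaluable.
- State that enrolment and replacement are decided without reference to response or confirmation status.
- Count patients with an unconfirmed response as non-responders in the denominator, consistent with SAP Table 2. Amend the exclusion wherever it appears (SAP 3.1 and 15.1, Protocol 7.0 and 22.2), so that evaluable N does not vary with confirmation.

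The cost is wording in the protocol and SAP, with no patients beyond the stated maximum. The sponsor gives up the option of topping up after seeing responses, and the reported ORR24 may be slightly lower.
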